4.4 Early Withdrawal of Subjects

4.4.1 When and How to Withdraw Subjects

A subject may be withdrawn from the study prior to the expected completion of that subject for safety reasons, failure of subject to adhere to protocol requirements, subject consent withdrawal, or subject is lost to follow up. Subjects will be deemed lost to follow up after a minimum of 3 documented phone calls, emails, or certified letters of a physician or designee at the study site to

the subject or emergency contact. If a participant is deemed lost to follow up, the PI or designee will mail a signed letter to the patient to inform them of their withdrawal from the study.

4.4.2 Data Collection and Follow-up for Withdrawn Subjects

All study procedures will be discontinued for the subject at the point of being classified as “Withdrawn.” Data collected up to the point of subject withdrawal may be used for analysis. If a patient is terminated early from the study as a result of an adverse event related to study procedures, every effort will be made to follow the patient until the adverse event resolves.

5 Study Drug

5.1 Description

Yohimbine is a potent selective α 2-adrenoceptor (AR) antagonist with weaker α 1-antagonist activity.

5.2 Administration Regimen

One yohimbine tablet (5mg) will be dispensed to the subject and administered orally at Visit 2.

5.3 Preparation and Administration of Study Drug

Yohimbine will be produced in a GMP compliant facility by CHEPLAPHARM ARZNEIMITTEL GMBH ([name]). The appropriate dose will be dispensed by the Investigational Pharmacy at Dartmouth-Hitchcock Medical Center and administered to the subject by a licensed clinician during Visit 2.

5.4 Subject Compliance Monitoring

Subjects will be asked to hold dopaminergic medications on the morning of Visits 1 and 2 and adrenergic medications for at least three half-lives on the mornings of Visit 1 and 2. If subjects do not comply with this, the visit will be rescheduled.

5.5 Prior and Concomitant Therapy

As part of each study visit, concomitant medications will be recorded and then reviewed. Subjects will be asked to hold levodopa and other dopaminergic medications for the morning of Visits 1 and 2. In addition, subjects may have to wean off or hold medications that interfere with autonomic testing and pupillary testing for Visits 1 and 2. Examples of medications that affect the NA axis and would have to be held for at least three half-lives include pyridostigmine, midodrine, stimulants (e.g. methylphenidate), venlafaxine, or droxidopa. This will be done with the guidance of their primary neurologists, with potential risks explained prior to patients agreeing to participate in this study. Subjects will only be enrolled if their primary neurologist feels that holding a medicine would represent minimal risk.

5.6 Packaging

Yohimbine preparation will be conducted in a GMP facility, CHEPLAPHARM ARZNEIMITTEL GMBH. Each package containing yohimbine will be pre-numbered with a lot number by the manufacturer prior to shipment and delivery to DHMC. The yohimbine hydrochloride tablets will be shipped to the Dartmouth-Hitchcock Investigational Pharmacy as 50 or 100 tablets in platelets (PVC / Aluminum) of 10 tablets

5.6.1 Receipt of Drug Supplies

Yohimbine will be shipped directly from CHEPLAPHARM ARZNEIMITTEL GMBH ([name]) to the Investigational Pharmacy at Dartmouth-Hitchcock Medical Center. Upon receipt of the study treatment supplies by the receiving pharmacy, the designated study staff will count and verify that the shipment contains all the items noted in the shipment inventory. Any damaged or unusable study drug in a given shipment will be documented in the study files.

5.6.2 Storage

Yohimbine will be stored at the Investigational Pharmacy at Dartmouth-Hitchcock Medical Center in a dry, cool location.

5.6.3 Dispensing of Study Drug

The yohimbine tablet will be dispensed at Visit 2. The Dartmouth-Hitchcock Investigational Pharmacy will keep record of all study drug issued. Notation will also be made in the participants' electronic medical records regarding the dispensation of the study drug

5.6.4 Return or Destruction of Study Drug

At the completion of the trial, a final reconciliation of study drug shipped, consumed, and remaining will be performed. This reconciliation will be logged on the drug reconciliation form, signed and dated. Any discrepancies noted will be investigated, resolved, and documented prior to destruction of unused study drug. All drug remaining at the completion of the study will be destroyed on site and will be documented in the study files.

6 Study Devices

6.1 Description of NeuroOptics® PLR-3000

All subjects will undergo pupillometric evaluation with the NeuroOptics® PLR-3000. The PLR-3000 system automatically measures monocular resting pupillary size using infrared light in a dark room, and then uses a brief light flash to measure minimum post-contraction pupillary size, contraction velocity, contraction latency, redilation velocity, and time of pupillary redilation. Pupillometric methods have been described previously⁷⁰⁻⁷² and will be modified for use with the NeuroOptics system. Testing will be done twice in each eye. Binocular pupillometric data collection will take less than 5 minutes to obtain. Bilateral results will be averaged for final

comparison. If there is a unilateral preexisting condition (e.g. untreated cataract), pupillometric evaluation will be limited to the unimpaired side with no averaging. We will measure these parameters at baseline with the patient at rest and room lights as dim as possible, then again with lights on. Pupillometry will be performed in the same room to maintain minimal variation in luminance. We will repeat these studies after yohimbine administration at the time of the second HUT.

7 Study Procedures

7.1 Schedule of Assessments

Event/Assessment	Visit 1			Visit 2 (occurs no more than 30 days after V1)		Follow-Up Phone Call (24-72 hours after Visit 2)
Informed consent	X					
Inclusion/Exclusion criteria	X					
Demographics	X					
Medical history	X					
History and current use of alcohol	X					
Current and prior smoking status	X					
UPDRS, Hoehn & Yahr staging	X					
Orthostatic vital signs (OVS)	X Baseline: holding L-dopa	X 30 min after L-dopa administration	X 1 hour after L-dopa administration	X pre yohimbine administration	X post yohimbine administration	
Serum Pregnancy Test (WOCBPO) ⁱ	X					

Event/Assessment	Visit 1			Visit 2		Follow-Up Phone Call (12 to 72 hours after Visit 2)
Urine Pregnancy Test (WOCBPO)				X		
Concomitant medications	X			X		X
Adverse Events	X			X		X
SCOPA-AUT	X					
HR and BP response to DB and Valsalva	X					
Vibrotactile detection thresholds	X					
Neurocognitive testing	X					
Neuropsychiatric assessment	X					
Neuropsychiatric assessment (Informant)	X					
Dynamic pupillometry	X (holding levodopa)		X (1 hour after levodopa administration)	X (pre yohimbine administration)	X (post yohimbine administration)	
C-SSRS Baseline Version	X					

Event/Assessment	Visit 1		Visit 2		Follow-Up Phone Call (12 to 72 hours after Visit 2)
CSSRS- Since Last Visit Version			X		
IV placement			X		
HUT			X (pre yohimbine administration)	X (post yohimbine administration)	
Visual analogue scales measuring anxiety, mood, fatigue			X pre -yohimbine administration	X post- yohimbine administration	
Serum AVP ⁱⁱ and NE ⁱⁱⁱ			X Pre Yohimbine administration	X Post Yohimbine administration	
Safety Labs (CBC, CMP) ^{iv}	X				

ⁱ Women of Child Bearing Potential Only

ⁱⁱ AVP will be draw after approximately 30 minutes supine and again at approximately 15 minutes upright tilt to 60 degrees.

ⁱⁱⁱ NE drawn after approx.30 minutes supine and again at approximately 5 minutes after upright tilt to 60 degrees

^{iv} If labs have been drawn within past 6 months and are WNL or with abnormalities that are NCS; those can be utilized for inclusion

7.2 Visit 1

- Informed consent
- Confirmation of Inclusion/Exclusion
- Demographic collection
- Medical History data collection
- Vital Signs
- Serum Pregnancy Test (women of childbearing potential only)
- Serum Safety Labs for CBC, CMP (if not completed in past 6 months)
- Orthostatic Vital Signs
 - Baseline, (holding AM dopamine)
 - Approx 30 minutes after dopamine administration
 - Approx 1 hour after dopamine administration
- Peripheral Nerve Testing
 - HR and BP response to DB and Valsalva
 - Vibrotactile detection thresholds
 - SCOPA-AUT survey
- Dynamic Pupillometry
 - Prior to dopamine administration
 - Approximately 60 minutes post-dopamine administration
- Neuropsychiatric and neurocognitive testing (approx. 1.5 hours in length)
- Columbia Suicide Severity Rating Scale, (Baseline)

Patients will be informed to hold dopaminergic medications on the morning of Visit 1 and adrenergic medications for at least three half-lives. After providing informed consent and meeting inclusion/exclusion criteria, subjects will be asked to complete a structured interview using a standardized questionnaire/data abstraction form to obtain demographic and clinical data. Information that the patient does not know will be obtained from the medical record and the patient's primary neurologist and entered into the standardized questionnaire/data abstraction form.

The following demographics and disease characteristics will be captured:

- Age, sex, race and ethnicity
- Income
- BMI
- Highest level of education completed
- H&Y staging
- Concomitant medications including levodopa and LDED

- Years since PD diagnosis
- Comorbidities (Charleston Comorbidity Index)
- Current and prior alcohol use
- Current and prior smoking status.

Subjects will also have their OVS done at baseline (holding AM dopamine) and then again at approximately 30 minutes and 1 hour after dopamine administration.

Neuropsychiatric and neurocognitive testing

Patients will complete on one occasion a battery of neurocognitive measures.

This will include:

- The Test of Premorbid Functioning (TOPF) , a word reading based estimate of premorbid IQ ⁷⁴
- Montreal Cognitive Assessment (MoCA) ⁷⁰
- Brief University of Pennsylvania Smell Identification Test (B-SIT) ⁷⁵
- Digit Span subtest from the Wechsler Adult Intelligence Scale – IV ⁷⁶
- Symbol Digit Modalities Test (Smith, 1968) ⁷⁷
- Trail Making Test ⁷⁸
- California Verbal Learning Test – II ⁷⁹
- Rey Complex Figure Test ⁸⁰
- DKEFS Color-Word Interference Test ⁸¹
- Phonemic and Semantic Verbal Fluency ⁸²
- Behavior Rating Inventory of Executive Function – Adult ⁸³

Patient neuropsychiatric characteristics will be assessed by having them complete on one occasion:

- The Geriatric Depression Scale (GDS) ^{84, 85}
- Geriatric Anxiety Inventory (GAI) ^{86, 87}
- Fatigue Severity Scale (FSS) ⁸⁸
- Apathy Evaluation Scale (AES) ^{89, 90}
- Activation-Deactivation Checklist to assess arousal (AD-ACL) ⁹¹

Patients will also complete a visual analogue scale before and after yohimbine to assess for acute changes in symptoms such as anxiety, fatigue, and concentration/attention [VAS; score ranging from 0% (no symptoms) to 100% (most severe symptom possible)]. ⁹⁵

An informant (when available) will complete informant report versions of the BRIEF-A, AES, as well as the Neuropsychiatric Inventory Questionnaire (NPI-Q). ⁹²

The total time for neurocognitive and neuropsychiatric testing will be approximately 1.5 hours.

Peripheral nerve testing:

This following peripheral nerve testing will performed by trained autonomic technicians and interpreted by the PI or a sub-I.

- HR and continuous BP variability monitoring with deep breathing and Valsalva.
- Patients will answer a validated survey to quantify their autonomic symptoms (the SCOPA-AUT).⁹³
- Measurement of vibrotactile detection thresholds.⁹⁴
- Dynamic pupillometry testing prior to subjects taking their levodopa-, and then again approximately 60 minutes after ingestion. See section 6.1 for pupillometry protocol.

7.3 Visit 2

HUT will be done first thing in the morning, since subjects will be holding their levodopa and other medications that could interfere with autonomic testing. Subjects will fast and abstain from coffee the morning of testing but will be encouraged to hydrate exuberantly.

[figure not shown]
Prior to beginning the HUT, the following will occur:

- Collection of adverse events since consent was signed /changes in medical history
- Collection of changes in concomitant medication will be collected.
- A C-SSRS, (Since Last Visit), will be also be performed.
- Urine pregnancy test will be performed prior to starting the HUT, (if a women is of childbearing potential,).

The following procedures will be performed as part of the HUT and measured per HUT protocol^{6, 22}, while under the supervision of a cardiac electrophysiologist, cardiology nurse and study coordinator.

- IV will be placed per standard HUT procedure.
- After approximately 30 minutes of supine rest:
 - Serum AVP and NE levels draw for baseline level
 - VAS scale completion for baseline/resting anxiety, fatigue and mood, ([VAS; score ranging from 0% (no symptoms) to 100% (most severe symptom possible)]⁹⁵).
- Pupillometric evaluations (see Figure 2).
- Tilt table to approximately 60 degrees for approximately 15 minutes; return to supine
- Yohimbine administration
- VAS scale completion for baseline/resting anxiety, fatigue and mood, ([VAS; score ranging from 0% (no symptoms) to 100% (most severe symptom possible)]⁹⁵).
- Patients will then be tilted to 60 degrees for a second time and remain in that position for approximately 15 minutes.
- NE will be drawn approximately 5 minutes after being tilted up to 60 degrees.
- AVP will be drawn approximately 15 minutes after being tilted up to 60 degrees.

Figure 2. Timeline of Visit 2

The total time for Visit 2 will be approximately **4-6 hours**, pending observation time post yohimbine administration (see Figure 2 above).

A cardiac electrophysiology sub-investigator, who will be trained in the protocol and drug effects, will monitor the tilt test, as well as halt the test in the unlikely case of dangerous syncope, arrhythmia, or intolerable symptoms. Yohimbine may even improve orthostasis.^{65, 66}

[name], or a designated sub-investigator, will be available via pager during all scheduled visit 2 activities. In the event of any adverse events during yohimbine administration and HUT, he will be available to assess and document any adverse effects clinically and identify a plan for clinical treatment, should any be necessary. Any adverse events occurring during yohimbine administration and HUT involving autonomic nervous system function and vital signs will be monitored for at least 3 hours post event to assure stable vital signs/condition.

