Subjects may have to wean off or hold medications that interfere with autonomic testing. This will be done with the guidance of their primary neurologists, with potential risks spelled out prior to patients agreeing to participate in this study. Subjects will only be enrolled if their primary neurologist feels that holding a medicine would represent minimal risk. Examples of medications that affect the noradrenergic axis and would have to be held for at least three half-lives include pyridostigmine, midodrine, stimulants (e.g. methylphenidate), venlafaxine, or droxidopa. Holding these medications could cause sleepiness, mild hypotension, increase appetite, anxiety, agitation, abnormal sweating, or other potentially bothersome symptoms, so their primary neurologists would need to approve participation when these medications are taken daily and need to be held.

Subjects will also hold food and coffee the morning of their tilt-table test, which might present a nuisance but not any significance risk since we are excluding patients with diabetes.

2 Study Objectives

Primary Objective is to explore the association between orthostatic hypotension (OH) and several neuropsychiatric and neurocognitive nonmotor features of Parkinson's disease (PD).

Secondary objectives include the following:

- To explore the association between central noradrenergic dysfunction, OH, and nonmotor symptoms of PD by measuring hormonal response to head up tilt-table (HUT) testing before and after administration of yohimbine
- To explore the association between central noradrenergic dysfunction, OH, and nonmotor symptoms of PD by measuring pupillometric parameters before and after administration of yohimbine

3 Study Design

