4.3 Subject Recruitment and Screening

Participation in this research requires informed consent according to Institutional Review Board (IRB) guidelines. A signed IRB approved Consent Form is the means of documenting this understanding. Subjects must be able to consent for themselves to be able to participate in this study and have received an exact copy (at point of signature acquisition). Potential recruits are instructed that their participation is voluntary and that their medical care will not be altered in any way should they elect not to participate.

Initial recruitment will take place during routine clinic visits with a DH neurologist caring for patients with PD. The study will be briefly described to the patient. If the patient is interested, a study coordinator will contact them to explain the study in detail and confirm eligibility. Interested subjects will then be sent informed consent information (i.e. study procedure, risks, and benefits) to review at home, and they will have the opportunity to ask questions prior to scheduling the first study visit. Completion of the informed consent process will then take place face-to-face at the onset of Study Visit 1, prior to any data collection. Data regarding the subject's UPDRS, H&Y standing and OVS will be gathered from the subject's medical record after consent has been obtained. All study visits and procedures will take place at Dartmouth-Hitchcock Medical Center, Lebanon, NH.

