The study period during which adverse events must be reported is normally defined as the period from the initiation of any study procedures to the end of the study treatment follow-up. For this study, the end of study treatment follow-up is defined as the completion of the follow-up phone call.

Preexisting Condition

A preexisting condition is one that is present at the start of the study. A preexisting condition should be recorded as an adverse event if the frequency, intensity, or the character of the condition worsens during the study period.

General Physical Examination Findings

At screening, any clinically significant abnormality should be recorded as a preexisting condition. At the end of the study, any new clinically significant findings/abnormalities that meet the definition of an adverse event must also be recorded and documented as an adverse event.

Post-study Adverse Event

All unresolved adverse events should be followed by the investigator until the events are resolved, the subject is lost to follow-up, or the adverse event is otherwise explained. At the last scheduled visit, the investigator should instruct each subject to report any subsequent event(s) that the subject, or the subject's personal physician, believes might reasonably be related to participation in this study. The investigator should notify the study sponsor of any death or adverse event occurring at any time after a subject has discontinued or terminated study participation that may reasonably be related to this study. The sponsor should also be notified if the investigator should become aware of the development of cancer or of a congenital anomaly in a subsequently conceived offspring of a subject that has participated in this study.

Abnormal Laboratory Values

A clinical laboratory abnormality should be documented as an adverse event if any one of the following conditions is met:

- The laboratory abnormality is not otherwise refuted by a repeat test to confirm the abnormality
- The abnormality suggests a disease and/or organ toxicity
- The abnormality is of a degree that requires active management; e.g. change of dose, discontinuation of the drug, more frequent follow-up assessments, further diagnostic investigation, etc.

Hospitalization, Prolonged Hospitalization or Surgery

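### Effects of the study-required drug hold before Visit 1 that are present or already over when consent is signed fall outside adverse event recording

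*Protocol*

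**What the plan says.** On the hold, Protocol Section 7.2 states: "Patients will be informed to hold dopaminergic medications on the morning of Visit 1 and adrenergic medications for at least three half-lives". Section 5.4 makes this a condition of the visit: "If subjects do not comply with this, the visit will be rescheduled". Sections 1.6 and 5.5 add that some patients may have to be weaned off drugs that interfere with testing.

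On its risks, Section 1.6 says of the drugs acting on the noradrenergic axis: "Holding these medications could cause sleepiness, mild hypotension, increase appetite, anxiety, agitation, abnormal sweating, or other potentially bothersome symptoms". For the dopaminergic hold it mentions stiffness and discomfort.

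On consent, Section 4.3 states: "Completion of the informed consent process will then take place face-to-face at the onset of Study Visit 1, prior to any data collection". Section 12 requires consent before a subject undergoes any study procedure.

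On AE recording, Section 9.1 gives the reporting period as normally the "period from the initiation of any study procedures to the end of the study treatment follow-up". For this study it then fixes the end (the follow-up phone call) but says nothing more about the start. The same section says: "A preexisting condition is one that is present at the start of the study". Such a condition becomes an AE only if its frequency, intensity or character worsens. At Visit 2, Section 7.3 calls for "Collection of adverse events since consent was signed /changes in medical history". The schedule in Section 7.1 also lists AEs at Visit 1.

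**The concern.** The study itself causes the first medication hold, and the protocol names symptoms that the hold may produce. The start of AE recording is nevertheless tied to consent and to the first procedure, both of which come after that hold has begun. Followed as written, the rules file a study-caused symptom under medical history, or do not ask about it at all.

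What is at stake is the safety record of the hold. Section 1.6 describes holding dopaminergic drugs as minimal risk and makes enrolment depend on the primary neurologist judging that holding a medicine is minimal risk. The AE data from the first hold would be an incomplete check on that judgement.

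**Working it through.** The protocol gives no figure on this point, so there is none to reproduce. The check is to put the events in order.

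1. **First hold.** It begins before arrival at Visit 1: that morning for dopaminergic drugs, at least three half-lives earlier for adrenergic drugs, and possibly earlier still where a drug is tapered (Sections 3.1, 5.4, 5.5, 7.2).
2. **Consent.** Signed on arrival at Visit 1, before any data collection (Section 4.3).
3. **AE period opens.** At the first study procedure (Section 9.1), which cannot precede consent (Section 12).
4. **Rest of Visit 1.** The dopaminergic hold continues for a time. Baseline orthostatic vital signs and pupillometry are taken before the patient takes the morning dose at the visit (Sections 3.1, 7.1, 7.2). AEs are collected at this visit (Section 7.1).
5. **Second hold.** Before Visit 2, hence after consent (Section 3.1).
6. **Visit 2.** AEs since consent are collected before the tilt test (Section 7.3).

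Applying the rules of Section 9.1 to each kind of hold effect:

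| Hold effect | Position relative to the window | Recorded as AE? |
|---|---|---|
| First hold, resolved before consent | Before it | No |
| First hold, present at consent, no worsening | Present when it opens | No; preexisting condition |
| First hold, present at consent, then worsens | Worsening is inside | Yes |
| First hold, begins after consent at Visit 1 | Inside | Yes |
| Second hold | Inside | Yes |

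Only the first two rows are lost. Section 9.1 points the same way under physical examination findings, where a clinically significant abnormality at screening is to be entered as preexisting. Low blood pressure found on arrival after a hold would fit that sentence.

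An illustrative record: agitation begins the day before Visit 1 during a hold and is still present, unchanged, at consent. It resolves once the drug is resumed, and returns during the second hold. There are two hold-related events. The first is a preexisting condition; the second develops during the study and is an AE. So 1 of 2 is counted.

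No sentence says outright that hold effects are to be coded as preexisting. The result comes from reading Sections 4.3, 7.2, 7.3, 9.1 and 12 together.

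**The case against.** The best counter-reading is that the hold is itself a study procedure, so that the Section 9.1 period already covers it. The wording of Section 9.1 does not rule this out: it does not mention consent, and it says only how the period is normally defined. But on that reading a procedure would precede consent, contrary to Section 12, and the Visit 2 look-back in Section 7.3 would still start at consent. The sections conflict either way.

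It is also fair to say that a symptom present on arrival can still be written down, because medical history is taken at Visit 1. It would then carry the wrong label and would not count as an AE. And no AE endpoint or AE comparison appears in Sections 3.2, 3.3 or 8.2, so the planned analyses do not change. Both points limit the weight of the issue but do not remove the gap.

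Three stronger readings are tempting, and the protocol does not support them.

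- A reader might infer that a symptom first seen before Visit 1 also goes uncounted when it returns at Visit 2. The second hold follows consent and lies inside the look-back. A symptom that resolved and came back develops during the study, or at least increases in frequency, and Section 9.1 counts either. Section 9.2 requires every AE in the period to be recorded.
- A reader might infer that half of all hold exposures (one of two holds per patient) are outside the window. The first hold straddles consent, exposures are not events, and nothing says that every patient takes a drug with the listed withdrawal effects.
- A reader might infer that the loss falls mainly on the group with orthostatic hypotension, because midodrine and droxidopa are among the drugs named. The protocol does not say who takes the held drugs, and its examples also include venlafaxine and stimulants.

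**Conclusion.** The point holds for the first hold only. Effects of that hold that have resolved by consent, or are present at consent and do not worsen, are not recorded as AEs, although the protocol lists effects of this kind as study risks. The consequence is under-recording of first-hold harms. Its size cannot be given as a count, because the protocol states neither how many patients take drugs that must be held nor how often hold effects occur. Data on the second hold will exist, so the safety of holding medication is not left wholly undocumented.

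The conclusion assumes that the hold is not itself a study procedure, which is what Section 12 implies if consent is signed on arrival. The change is worth making because the gap follows from the stated rules and closing it costs little.

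**What to change.** - In Section 9.1, state that a symptom starting or worsening during a study-directed medication hold or taper is an AE and not a preexisting condition. Open the AE period at the first dose withheld or tapered for the study.
- In Section 7.3, align the Visit 2 look-back with that definition.
- At Visit 1, after consent, add one question that records the start date of the hold and the onset date of any symptom. AEs are already scheduled at this visit, and nothing is collected before consent.
- Reconcile Sections 4.3, 7.2, 9.1 and 12 on whether the hold counts as a study procedure. Redefining the AE period does not settle that by itself.

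These changes concern recording only and leave the hold as it is. The cost is protocol and case report form wording, one extra question, and a slightly higher reported AE count.
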